3.1 Medical and scientific background

Anastomotic insufficiencies and oesophageal perforations are life-threatening, severe complications of the upper gastrointestinal (GI) surgery. The reported incidence of anastomotic leaks overall is between 5% and 25%. Depending on the position and dimensions of the leaks, they are associated with a mortality of up to 60% [28]. Therapy of patients who experience symptomatic intrathoracic anastomotic leaks is usually difficult and carries a high risk of severe secondary complications. Depending on the severity of the anastomotic leakage, the time interval after primary surgery, the general condition of the patient and the anastomotic location, several treatment strategies are available, such as conservative, endoscopic or surgical treatment. Conservative treatment approach includes strict nil per oral, drainage and i.v. antibiotics. Surgical treatment options span from the reexecution of the anastomosis with augmentation of the anastomotic area by vital tissue (e.g. muscle flap, omental flap), to complete surgical deviation by taking down the oesophageal conduit and creation of a cervical stoma. Endoscopic methods include injection of fibrin glue and clip administration, introduction of self-expanding metal or plastic stents and endoluminal vacuum therapy.

As one can see already from the number of possible options, no general treatment of choice or standardized treatment algorithm exists so far. Each method has its pros and contras. While some surgeons recommend aggressive surgery, others prefer conservative approaches, including peri-anastomotic drainage, total parenteral nutrition, nasogastric decompression, and use of broad-spectrum antibiotics. Also, although introduction of self-expanding metallic coated stents was regarded as a considerable advancement in treatment of thoracic anastomotic leaks, their usage does not always lead to a sufficient sealing of the leakage, and dislocation rates up to 30% have been reported [27]. Another limiting factor for the stent placement may be a need for additional surgical interventions to provide drainage and removal of the septic focus [25, 27, 31].

Colorectal anastomotic leakage (CAL) also remains a frequent and dangerous complication after gastrointestinal surgery, occurring in 4-33% of patients and contributing to one third of postoperative mortality. An anastomotic defect causes leakage of colonic content into the abdominal or pelvic cavity, leading to peritonitis, abscess formation or sepsis. CAL substantially (by 1-2 weeks) prolongs hospital stay and increases medical costs by as much as US\$24,000 within the first period of hospitalisation, thereby approximately tripling the expenditure in comparison to that of a normal recovery. Moreover, CAL is identified as a risk factor for local recurrence of colorectal cancer and is reported to reduce long-term cancer specific survival. The type of intervention strongly depends on the severity of CAL, which is hard to determine, and therefore the choice of intervention for a suspicious leakage is quite complex with very limited evidence-based strategy available at present. Colorectal surgeons use various methods, i.a. conservative follow-up, adhesive materials (e.g. cyanoacrylate), abscess drainage, open pelvic lavage, construction of an entirely new anastomosis, and endoscopic or surgical interventions, such as diverting or ending the stoma and transanastomotic continuous drainage system with negative pressure.

3.2 Rationale

Endoscopic (endoluminal) vacuum therapy (EVT), alternative term endoscopic vacuum-assisted closure (EVAC), was for the first time applied in Europe by Weidenhagen et al. [31] in 2003 for use in the rectum and in 2007 by Loske et al. [12] for use in the foregut.

Loske et al. [13] summarized the experience of EVT for patients with anastomotic insufficiency secondary to esophagectomy or gastrectomy (n=5), iatrogenic oesophageal perforation (n=2), oesophageal wall necrosis (n = 1), Boerhaave's syndrome (n=1), and perforation of oesophageal cancer (n=1). After one to seven changes of the sponge at intervals of 2–7 days and a mean therapy duration of 12 days, the defects were healed in all the surviving patients (n=9). One patient died of intercurrent severe colitis. In three cases, a revision laparotomy was necessary at the beginning of treatment. No post-interventional stricture or functional relevant scar formation was observed during a follow-up period of 10 - 380 days after termination of the vacuum therapy.

In a pilot study of EVT in the upper GI tract, conducted by Ahrens et al. [1], four patients with thoracoabdominal oesophagus resection and one patient with myotomy of Zenker's diverticulum were successfully treated till closure of their leakages without a need for surgical re-intervention. Two patients required endoscopic dilation of moderate anastomotic stenosis after completion of EVT.

Wedemeyer et al. [30] could demonstrate successful use of EVT in the management of major postsurgical gastrooesophageal intrathoracic leaks (prospective single-centre study with 8 patients). Leakage closure by EVT was achieved in 7 cases, EVT could not be completed in one case due to safety concerns. No SAEs associated with the endoscopic intervention or EVT were noted. Complications observed: patients reported discomfort in the nose and throat (n=8), sponge dislocation (n=2).

In the retrospective analysis by Brangewitz et al. [6], comparing EVT versus stent management (self-expanding metal (SEMS) or plastic stents (SEPS)), data of 39 patients who were treated with SEMS or SEPS and 32 patients who were treated with EVT for intrathoracic leakage were analysed. Successful wound closure was independently associated with EVT (hazard ratio 2.997, 95% confidence interval [95%CI] 1.568–5.729; P=0.001). The overall closure rate was significantly higher in the EVT group (84.4%) compared with the SEMS/SEPS group (53.8%). No difference was found for hospitalisation and hospital mortality. Significantly more strictures were observed in the stent group (28.2% vs. 9.4% with EVT, P<0.05). Complications in the stent group constituted: stent dislocation (n=6), anastomotic stricture (n=11), severe bleed at the upper end of the stent followed by immediate surgical revision (n=1), oesophageal necrosis with fatal outcome (n=1), self-limiting bleeding after stent-removal (n=2), ulcers after stent removal, not requiring specific therapy (n=5). Complications in the EVT group constituted: sponge dislocation (n=5), bleeding after sponge removal (n=1), significant mucosal tear proximal to the anastomosis during sponge removal (n=1), bronchooesophageal fistual with later required surgery (n=1), anastomotic stricture (n=3).

Heits et al. [8] analysed data of 10 patients, treated by EVT for oesophageal perforations, located in the cervical (n=3) and thoracic (n=7) oesophagus. Complete healing of the wound was achieved in 9 cases. One patient has died (failure of the cardiovascular system caused by a known heart insufficiency). EVT-associated complications (mediastinal emphysema) occurred in 7 patients.

Bludau et al. [4] summarized the experience of EVT for patients with oesophageal leakages (n=14). For 6 of 14 patients, EVT was combined with a placement of self-expanding metal stents. Complete closure of the

oesophageal defect was achieved in 12 cases. Two patients died due to prolonged sepsis before EVT could be completed. In two cases, oesophageal stenosis was diagnosed, which was treated successfully by one-time pneumatic dilation. No other complications related to the EVT were observed.

Strangio et al. [26] evaluated performance and safety of EVT in 25 patients with partial colonic anastomotic leakage. Complete healing was achieved in 22 cases. Three patients developed a major complication (1 ure-teric fistula, 1 ileal fistula, and 1 pararectal abscess), all successfully treated by surgery. Ileostomy closure was achieved in 11 patients. No mortality related to the procedure was observed.

In a retrospective study including 15 patients with pelvic anastomotic leakage after colorectal surgery [9], lumen integrity was achieved in 12 cases. Treatment was discontinued due to progression of pelvic sepsis in two patients and due to bleeding in one patient. No complications, related to the EVT, were reported.

In a study of EVT by upper gastrointestinal leaks and perforations, conducted by Smallwood et al. [25], complete closure of perforation or leak after an average of 35.8 days of EVT was demonstrated for all patients (n=6). No deaths occurred within 30 days following EVT. One patient died following complete closure of his perforation and transfer to an acute care facility due to an unrelated complication. There were no complications directly related to the use of EVT.

Mennigen et al. [20] compared 30 patients, treated with stent insertion, with 15 patients, treated with EVT for management of oesophageal anastomotic leakage following oesophagectomy, performed with a stapled intrathoracic anastomosis (end-to-side, circular stapler). The rate of endoscopic anastomotic healing was found to be higher for endoscopic vacuum therapy (93.3%, vs. 63.3% in a stent group; P=0.038). No significant difference was observed for overall mortality, duration of therapy, and length of hospitalisation.

In a prospective cohort study [11] including 52 patients with oesophageal anastomotic insufficiencies of different origin, healing of the oesophageal wall defects in 49 cases was observed (in 7 cases, final closure was performed by additional clipping of residual superficial defects with an Over-The-Scope-Clip [OTSC]). One patient showed no response to EVT and two patients died due to haemorrhage related to the procedure. Postinterventional stricture was observed during follow up period in 4 patients.

In a retrospective review of case series [3], endoscopic vacuum therapy was applied in 14 patients with colorectal leak. Overall success rate was 79%, favored by early beginning of treatment. Median duration of treatment was 12.5 sessions (range 4 - 40). Median time for complete healing was 40.5 days (range 8 - 114). No EVT-related complications were observed.

The effectiveness and safety of EVAC therapy was verified in a study including 55 patients with anastomotic leakage in the upper GI tract [32]. Patients underwent elective oesophageal resection and EVAC (intracavitary or intraluminally) was initiated. Sponge changes were performed either every 3 days for intracavitary localization or every 5 - 7 days for intraluminal position. Successful closure was achieved in 49 patients (n=49) while complication rate was 5.4 % (n=3). One patient suffered from bleeding while 2 patients had minor sedation-related complications. Median number of EVAC procedures was 3 with median 14-day duration of therapy. Mortality rate was 7.2 % (n=4); 3 patients died despite of complete healing due to multiple organ failure, acute respiratory distress syndrome and urosepsis.

In the prospective, observational, national, multicenter registry of Eso-Sponge® for anastomotic leakage after esophageal resection or perforation (23) a success rate of 91 % was demonstrated.

In 2019, Loske (18) summarized the data from 18 studies (420 patients worldwide) in which more than five patients were treated with endoscopic negative pressure therapy in the upper gastrointestinal tract, and the success rate was found to be 87% (range 60-100%).

A systematic search of MEDLINE/PubMed and Cochrane databases (10) was performed by Kühn et al. using search terms related to EVT and colorectal defects (anastomotic leakage, rectal stump insufficiency) according to the PRISMA guidelines. Randomized controlled trials (RCTs), observational studies, and case series published by December 2020 were eligible for inclusion. A meta-analysis was conducted on the success of EVT, stoma reversal rate after EVT as well as procedure-related complications. Twenty-four studies reporting on

690 patients with colorectal defects undergoing EVT were included. The mean rate of success was 81.4% (95% CI: 74.0%-87.1%). The proportion of diverted patients was 76.4% (95% CI: 64.9%-85.0%). The mean rate of ostomy reversal across the studies was 66.7% (95% CI: 58.0%-74.4%). Sixty-four patients were reported with EVT-associated complications, the weighted mean complication rate across the studies was 12.1% (95% CI: 9.7%-15.2%).

Also, numerous case reports and case series describe the successful usage of EVT for closure of oesophageal [7, 14, 15, 16, 17, 21, 30] and rectal [2, 5] defects.

Only limited evidence for comparison of different treatment approaches for both upper and lower GI tract defects can be found in literature. To compare EVT of leakage after oesophagectomy with other therapy regimes, Schniewind et al. [24] analysed 62 patients, who have developed an anastomotic leak. Therapy options included surgical revision (n=18), endoluminal vacuum therapy (n = 17), endoscopic stent application (n=12), and conservative management (n=15). In-hospital mortality constituted 26% (of which EVT 12% [n=2], surgery 50% [n=9], stent 42% [n=5], 0% of the conservatively treated patients). The survival in the EVT group was significantly superior to that of the surgically treated patients (p = 0.011, log rank test) and to that of the stented patients with oesophageal leakage (p =0.00014, log rank test). To summarize, this study suggests that EVT is an effective procedure for a management of major leakage from oesophageal anastomoses and might be superior to surgical revision and stent placement, especially in septic patients. However, it is obvious that this data should be further confirmed on bigger patient population.

In the study by Mees et al. [19] comparing patients treated with EVT (n=5: rectal carcinoma n=3, ulcerative colitis n=2) vs. transrectal lavage (n=5: rectal carcinoma n=3, ulcerative colitis n=2) after colorectal resection, median time of defect closure constituted 45 days in the EVT group, compared to 101 days in the lavage group. Average time in the hospital constituted 37 and 45 days, respectively. EVT was well tolerated by all patients and no specific side effects during or after the therapy were observed. One patient in the EVT group developed a mild rectal stenosis in the anastomotic area during the follow-up. This stenosis was treated by self-dilatation using Hegar's dilator for 4 weeks. Overall costs were summarized for both procedures considering the differences in the number of sessions (EVT - 7 replacements/ patient; lavage - 12 procedures/ patient), costs for staff and material. This resulted in comparable costs of $122.85 \in (EVT)$ vs. $119.4 \in (lavage)$, respectively.

Though a number of studies and case reports have demonstrated promising results regarding efficacy of EVT in treatment of both upper and lower GI tract perforations and anastomotic insufficiencies, and, potentially, even better safety profile of this treatment in comparison with other conventional treatment methods, the amount of data is still relatively small and additional data collection and analysis is necessary.

4. Benefits and risks of investigational device, clinical procedures and clinical study

All medical devices used in this study are CE-marked, marketed devices which will only be used in line with the approved IFU in the intended patient population.

4.1 Anticipated clinical benefits of investigational devices

Patients requiring EVAC are considered to be in a life-threatening condition due to the possibility of developing mediastinitis, peritonitis as well as consecutive sepsis with fatal outcome. With regard to the benefits of Suprasorb[®] CNP endo, review of current literature allows the conclusion that safety and tolerability of the IP are acceptable. Therefore, the IP can be considered suitable for the management of endoluminal wounds including perforations and anastomotic leakages. There is sufficient clinical evidence to declare conformity of the device with the general safety and performance requirements.

4.2 Anticipated adverse effects of investigational devices

4.2.1 Side effects

The biocompatibility of Suprasorb[®] CNP endo can be classified as acceptable for the intended purpose and application. Suprasorb[®] CNP endo is made of materials which have been well-characterised chemically and physically in the published literature. Overall, the combination of non-clinical and clinical data on Suprasorb[®] CNP endo demonstrates that Suprasorb[®] CNP endo devices are suitable for their intended purpose and confirms that the clinical benefits of the device outweigh theoretical and known risks.

The most common complications recorded for the devices are, e.g. pain, nasal bleeding and mediastinal emphysema. However, the devices showed to be feasible and well-tolerated device for EVAC. It should be kept in mind that patients requiring EVAC are considered to be in a life-threatening condition due to the possibility of developing mediastinitis, peritonitis as well as consecutive sepsis with fatal outcome.

4.2.2 Interactions

None known.

4.3 Effects of study participation

4.3.1 Anticipated risks of study participation

Participation does not pose additional risks compared to routine clinical care because there are no study interventions in this purely observational clinical study. Participation just means following routine clinical care decisions and procedures but allowing to use available medical data in a central study database.

- All medical devices used in this study are marketed products used in clinical routine care in line with market authorisation and represent standard of care in this therapeutic indication. This also applies to all medical procedures within the study.
- This clinical study is purely observational. The study protocol does not define any study-specific intervention or procedure to be performed. The only study-specific obligation within this observational study is to document pre-defined medical and procedural data if available in routine clinical care at a level of data quality following international standards on clinical studies.
- All therapeutic decisions and procedures are performed as routine clinical care following all applicable ethical and regulatory standards. Therefore, adverse events will occur in clinical manifestations and at rates as in routine clinical care.
- The study will be conducted in accordance with the principles laid down in the Declaration of Helsinki in its version of October 2013 (Fortaleza) and in accordance with ISO 14155:2020.
- Before initiating the study in a country, approval of the corresponding Ethics Committees (ECs) will be obtained.

4.3.2 Anticipated benefits of study participation

No to minor additional benefit will be added for patients participating in this purely observational clinical study.

 All therapeutic decisions and procedures are following individual decisions of the treating physician and are performed as routine clinical care. Thus, no additional benefit compared to routine clinical care will occur because all procedures are routine clinical care. Little additional benefit might occur based on standardised data documentation and queries related to data entries provided by a third party (e. g. a contract research organisation) which both might lead to more standardised routine clinical care procedures and decisions.

4.4 Possible interactions with concomitant medical treatments

None known.

4.5 Steps that will be taken to control or mitigate the risks

All therapeutic decisions and procedures are following individual decisions of the treating physician and are performed as routine clinical care practice following applicable medical standards. All relevant safety information concerning residual risks is provided to the user in the product labelling and instructions for use. This comprises contraindications, side effects, warnings and precautions.

The study protocol does not define any study-specific intervention or procedure to be performed. Therefore, adverse events representing the potential risks are expected to occur in clinical manifestations and at rates as in routine clinical care. The investigator will promptly report to the sponsor serious adverse events and adverse device effects according to 14.3. The sponsor will, based on these data, perform actions in case of hazards and foreseeable damage to patients and report promptly to regulatory bodies according to 14.3.

4.6 Rationale for benefit-risk ratio

The study is purely observational with documentation of routine clinical care procedures and outcomes, without adding any study specific interventions or procedures. Thus, the structural risk of the study defines as low, i.e. not exceeding the risk of use of Suprasorb[®] CNP endo in routine clinical care.

From Clinical Evaluation Report (DI_CER_00020_02, Feb 2022) and risk management perspective it can be concluded that the benefit / risk ratio for Suprasorb[®] CNP endo is positive.

5. Objectives and hypotheses of the clinical study

5.1 Purpose of the clinical study, claims for clinical performance, effectiveness or safety of the investigational device

5.1.1 Purpose

The study is performed as observational PMCF study to generate in the setting of routine clinical care reliable data on the therapeutic approach of Suprasorb[®] CNP endo used in adult patients for negative pressure therapy in the oesophagus and rectum to support defect and wound healing. It will comply with the requirements set out by the clinical data requirements of EU MDR 2017/745.

5.1.2 Claims for clinical performance and effectiveness

The Suprasorb[®] CNP endo claims to support defect and wound healing in the upper and lower gastrointestinal tract by draining body fluids and simultaneously provide the possibility of enteral feeding for the upper gastrointestinal tract. Defects like perforations (iatrogenic perforations, spontaneous perforations), anastomoses and anastomotic insufficiencies can be treated intraluminal and/or intracavity with Suprasorb[®] CNP endo.

5.1.3 Claims for clinical safety

There is sufficient clinical data to declare conformity of the IP with the general safety and performance requirements with a positive benefit / risk ratio.

5.2 Objectives

The objectives of this PMCF study are to confirm performance and safety of Suprasorb[®] CNP endo in routine clinical care by evaluation of clinical data after market approval, including detection of potential unexpected adverse events associated with its use within the certified indications and under the conditions of routine clinical care. This will be assessed in defects of different aetiology in the oesophagus and rectum, thus, widely representing routine clinical care population and use.

5.2.1 Primary objective

To assess in a routine clinical care setting the performance of Suprasorb[®] CNP endo regarding wound healing in patients with oesophagus and rectum defects of different aetiologies.

Wound healing is defined as release for oral food intake (in upper GI tract use) or endoscopic release for stoma relocation (in lower GI tract use).

Time to wound healing is consequently defined as time from index use of Suprasorb[®] CNP endo to date of release for oral food intake (in upper GI tract use) or endoscopic release for stoma relocation (in lower GI tract use).

5.2.2 Secondary objectives

To assess in a routine clinical care setting in this patient population

- 1. adequate safety of the use of Suprasorb[®] CNP endo, and
- 2. duration of hospital care with use of Suprasorb[®] CNP endo.

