6.1.3 Endpoints of the study

6.1.3.1 Primary endpoint

Time period in days from index use of Suprasorb[®] CNP endo to release for oral food intake (in upper GI tract use) or endoscopic release for stoma relocation (in lower GI tract use).

In case of lower GI tract use and no stoma present, time period to release for oral food intake is the relevant endpoint.

6.1.3.2 Secondary endpoints

- 1. Number of SAEs related to defect treatment within total observation period.
- 2. Number of nights in hospital for therapy of index defect.
- 3. Number of nights at the ICU during hospital stay for therapy of index defect.

Nights at an intermediate care unit (IMC) will not count for this secondary endpoint.

SAEs will be adjudicated by an independent Clinical Event Committee (CEC) according to standard definitions. Wherever reasonable, endpoints will be normalised to one year of follow-up to adapt results to varying follow-up periods.

"Index defect" describes for each study patient the defect(s) which lead to the clinical indication of treatment with Suprasorb[®] CNP endo system according to IFU and medical guidelines as defined in 6.3.1.

"Index therapy" describes for each study patient the first use of Suprasorb[®] CNP endo for therapy of the index defect.

6.1.4 Methods and timing for assessing, recording, and analysing variables

Only data which can be obtained from routine clinical care files of the patients will be recorded. Data of routine clinical care visit after study enrolment will be reported in the e-CRF. Data will be derived from clinical records and findings, radiological assessments, observations or other sources (e.g. hospital records, clinical and office charts, electronic patient records, laboratory notes).

Within this observational study timing of measures and clinical data to be reported are determined by routine clinical care in line with applicable medical guidelines and local policies. The study protocol just defines some procedural recommendations.

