6.4.4 Treatment of the index defect

The decision of treatment of the index defect lies with the treating physician in routine clinical care. Indication as well as initiation of treatment should follow applicable medical guidelines, local clinical care policy and the IFUs of the devices used.

Initiation of treatment might start as routine clinical care procedure before enrolment into the study (i.e. informed consent of the patient) but data can be entered into the e-CRF after signed informed consent is available (i.e. after enrolment), only.

- Primary EV therapy is defined as the utilisation of EVT as first-line therapy for perforation or leak.
- **Rescue EV therapy** is defined as EVT placement following failure of definitive surgical repair for a perforation or leak.
- **Defect closure following EVT placement** is defined as 1) no evidence of continued leak under direct endoscopic visualization and 2) a negative oesophagram following discontinuation of EVT therapy.

Data regarding index defect, related therapy and outcome following EVT placement will be documented in the e-CRF at the Index-treatment visit.

The following data items will be documented of each participating patient at the index-treatment visit:

- Data of index treatment and related therapy (defect size, type and location of perforation, pre-existing pathology, ASA-classification, Perforation Severity Score (PSS), primary or rescue EVT application, type of endo-sponge placement, type of surgical repair, time to placement of EVT following diagnosis, number of EVT changes, number of days between EVT changes, total length of EVT therapy, relevant laboratory parameters)
- Outcome of index treatment (including 30-day mortality, closure interventions following treatment of index defect, hospital length of stay (LOS), ICU LOS, EVT therapy-specific findings (e.g. migration, dislodgement, erosion), time to oral diet initiation / endoscopic release for stoma relocation following successful defect closure).

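### The primary event is a release with no requirement that it lasts, and Section 6.4.4 adds a closure condition that the endpoint text lacks

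*Protocol*

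**What the plan says.** The primary objective (5.2.1) is performance regarding wound healing, and it equates healing with a release: "Wound healing is defined as release for oral food intake (in upper GI tract use) or endoscopic release for stoma relocation". The clock follows from that: "Time to wound healing is consequently defined as time from index use of" the device to the date of release. The primary endpoint (6.1.3.1) is the number of days from index use "to release for oral food intake (in upper GI tract use) or endoscopic release for stoma relocation (in lower GI tract use". For some rectal patients the event changes: "In case of lower GI tract use and no stoma present, time period to release for oral food intake is the relevant endpoint". None of this text mentions closure of the defect, recurrence, or withdrawal of a release.

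Section 6.4.4 lists the data item that supplies the endpoint, and there it carries a condition: "time to oral diet initiation / endoscopic release for stoma relocation following successful defect closure". Closure is defined in the same section by two criteria: "no evidence of continued leak under direct endoscopic visualization" and "a negative oesophagram following discontinuation of EVT therapy". The section also collects "closure interventions following treatment of index defect".

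The assessment table in 6.4.5 places the outcome of index treatment at the index-treatment visit only. Follow-up visits collect patient status, medication or other treatment (both only when the visit is on site) and safety events. The Clinical Event Committee (1.2, 14.1) reviews serious adverse events, adverse events of special interest and hospitalisations. Reviewing the release is not among its tasks.

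**The concern.** Release is decided by the treating physician, who knows the treatment, under local policy, and it is the only event in a test that Section 7 calls confirmatory. Take a patient who is released, leaks again, and returns to fasting or renewed vacuum therapy. That patient did not have the wound healing named in the objective, yet meets the endpoint wording on the release date.

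The one-sample log-rank test compares observed with expected events. A release that does not last adds an observed event and ends the patient's contribution to the expected count, and both effects push towards superiority. The reference was built on stoma relocation, a completed procedure, while study patients are scored on permission for it.

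The record may also be too thin to repair this later. A release withdrawn after discharge that causes no serious event and no listed complication may leave no dated entry in the e-CRF.

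**Working it through.** **Passages side by side.**
- 5.2.1 and 6.1.3.1: event = release; no closure condition; no durability condition.
- 6.4.4: recorded time = release after successful closure. Closure is checked at one point in time, so it can screen out a release before closure but not a recurrence afterwards.
- The second closure criterion is an oesophagram, which has no meaning for a rectal defect. Section 6.3 plans about equal numbers of upper and lower GI patients, so for about half the study the closure condition cannot be applied as written.

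**Plan figures used (6.3.7).** The reference proportion reproduces: the rise from 50% to 75% over 4 to 13 months is 25/9 = 2.8% per month, and 50 + 2 × 2.8 = 55.6, or 56% at 6 months. Enrolment reproduces: 99/0.90 = 110. The stated 13 expected events do not follow from 75% and 56% read as event proportions, which give about 50 events in 99 patients over 3 months under the 75% assumption. That is a separate matter, and 13 is not used below.

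**Set-up.** Exponential times (Weibull shape 1, as in 6.3.7), 99 patients, 3 months each, two-sided 4.92% (critical value about 1.97), interim look ignored. Lasting release follows the reference exactly, so there is no true benefit. The share of first releases later withdrawn (5, 10, 15%) is an assumption.

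- Reference hazard: λ = −ln(0.44)/6 = 0.1368 per month.
- Lasting releases within 3 months: 99 × (1 − e^(−0.1368 × 3)) = 99 × 0.3367 = 33.3. With no withdrawals, observed and expected counts are both 33.3.
- Statistic: Z = (O − E)/√E.

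**Case A: no withdrawn patient heals again within 3 months.** Withdrawn releases are placed evenly between 0.2 and 2 months (mean 1.1). At 10%:
- extra events = 33.3 × 0.10/0.90 = 3.7, so O = 37.0;
- expected count lost per withdrawn patient = 0.1368 × (3 − 1.1) = 0.26, so E = 33.3 − 3.7 × 0.26 = 32.4;
- mean shift of Z ≈ (37.0 − 32.4)/√32.4 = 0.8 standard errors.

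**Case B: every withdrawn patient heals again within 3 months.** The earlier release is placed at a random fraction of the final time. O stays at 33.3. The mean lasting-release time among those healed is 1/0.1368 − 3 × 0.6633/0.3367 = 1.40 months. At 10%, E falls by 3.33 × 0.5 × 1.40 × 0.1368 = 0.32, a shift of about 0.32/√33.0 = 0.06 standard errors.

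Simulated chance of a significant result favouring the device (20,000 trials per setting; repeat runs differ by a few tenths of a point in case B and by a point or two in case A):

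| First releases withdrawn (assumed) | A: none heals again | B: all heal again |
|---|---|---|
| 0% | about 3% | about 3% |
| 5% | 7% | 3.4% |
| 10% | 14% | 3.7% |
| 15% | 27% | 4.0% |

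The base is about 3% and not 4.92/2 = 2.46% because the normal approximation is slightly anticonservative in this tail.

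An intermediate mechanism, in which a share of all patients is released at half the time of their lasting healing, gives 5.4% at a 5% share, 8.4% at 10% and 18% at 20%.

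**The case against.** Several counter-arguments have weight.

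- A reader might infer that the protocol has a rule scoring the first release even after it is withdrawn. It has none. The word first does not appear, and no sentence says a withdrawn release still counts. This comes from silence, and the announced SAP may settle which date is used. That stands as a limit on the wording. It does not remove the point, because the protocol itself fixes the primary event, an unqualified event date in a time-to-event analysis is naturally the first one, and an SAP cannot use a withdrawal date that was never collected.
- A reader might infer that unverified, premature releases count freely. Section 6.4.4 argues against this, since it ties the recorded time to closure, and release for stoma relocation is itself endoscopic. This stands: recurrence after closure is the main gap, together with the mismatch between sections.
- Failures are not invisible. A readmission adds nights in hospital and possibly in the ICU (secondary endpoints 2 and 3), and fistula, abscess, peritonitis and mediastinitis are events of special interest. This is true, but none of it changes the primary result.
- The larger error rates require that nobody heals again. This stands, and case B is therefore shown beside case A.
- The bias assumes that the reference counts lasting events. The protocol says only that it counts stoma relocation. If the source counted events that were later reversed, the bias would be smaller, and requiring lasting release could count against the device.

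**Conclusion.** The point holds in this form: the endpoint text has no durability condition, it differs from 6.4.4 on closure, and read literally it credits healing to a patient whose release is withdrawn after recurrence. The direction favours the device. The size is uncertain, because the protocol gives no withdrawal rate. With 5 to 15% of first releases withdrawn, the chance of false superiority lies between almost no change (3.4 to 4.0%) and a serious inflation (7 to 27%), against about 3%, depending on how many patients heal again within 3 months. These figures rest on 99 patients, 3 months of follow-up, exponential times, a 56% reference at 6 months that counts lasting events, and no true benefit. The upper end should not be read as the expected case. The change is worth making because it is cheap and the claim is confirmatory. The documents do not show that the result would be invalid without it.

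**What to change.** 1. Reconcile 5.2.1 and 6.1.3.1 with 6.4.4, so that all three state the same event, including what documented closure means for rectal defects.
2. Define the primary event as release after documented defect closure that is not followed, within the observed follow-up, by documented withdrawal of the release or by renewed vacuum or closure treatment of the index defect. If it is so followed, the date of the last lasting release counts; if there is none, there is no event.
3. Add an e-CRF item for withdrawal of release, with its date, at the index-treatment visit and at every follow-up visit, including the telephone contact.
4. Report the analysis by first release alongside as a sensitivity analysis.

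The cost is a few sentences of endpoint text and one e-CRF item; patient care does not change. The event count will be slightly lower. Late releases have a shorter window in which withdrawal can be seen, since follow-up ends 3 months after discharge. The report should state this as a limitation.
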